14.4.2 Shift Tables

Table 14.4.2.1 Safety Laboratory Shift Tables

Parameter:	Parameter: e.g., Hemoglobin											
	PraB 40 (n = xx) Baseline				PraB 20 (n = xx) Baseline				OnaB 20 (n = xx) Baseline			
Timepoint	Low	Normal	High	Total	Low	Normal	High	Total	Low	Normal	High	Total
Final Visit												
Low	xx (x.x%)	xx (x.x%)	xx (x.x%)	xx (x.x%)	xx (x.x%)	xx (x.x%)	xx (x.x%)	xx (x.x%)	xx (x.x%)	xx (x.x%)	xx (x.x%)	xx (x.x%)
Normal	xx (x.x%)	xx (x.x%)	xx (x.x%)	xx (x.x%)	xx (x.x%)	xx (x.x%)	xx (x.x%)	xx (x.x%)	xx (x.x%)	xx (x.x%)	xx (x.x%)	xx (x.x%)
High	xx (x.x%)	xx (x.x%)	xx (x.x%)	xx (x.x%)	xx (x.x%)	xx (x.x%)	xx (x.x%)	xx (x.x%)	xx (x.x%)	xx (x.x%)	xx (x.x%)	xx (x.x%)
Total	xx (x.x%)	xx (x.x%)	xx (x.x%)	xx (x.x%)	xx (x.x%)	xx (x.x%)	xx (x.x%)	xx (x.x%)	xx (x.x%)	xx (x.x%)	xx (x.x%)	xx (x.x%)

Shift from Baseline

(x.x%) = proportion of subjects

Table 14.4.2.2 ECG Shift Tables

Parameter: e.g., PR Interval												
	PraB 40 (n = xx) Baseline			PraB 20 (n = xx) Baseline				OnaB 20 (n = xx) Baseline				
Timepoint	Normal	Abnormal (NCS)	Abnormal (CS)	Total	Normal	Abnormal (NCS)	Abnormal (CS)	Total	Normal	Abnormal (NCS)	Abnormal (CS)	Total
Final Visit												
Normal	xx (x.x%)	xx (x.x%)	xx (x.x%)	xx (x.x%)	xx (x.x%)	xx (x.x%)	xx (x.x%)	xx (x.x%)	xx (x.x%)	xx (x.x%)	xx (x.x%)	xx (x.x%)
Abnormal (NCS)	xx (x.x%)	xx (x.x%)	xx (x.x%)	xx (x.x%)	xx (x.x%)	xx (x.x%)	xx (x.x%)	xx (x.x%)	xx (x.x%)	xx (x.x%)	xx (x.x%)	xx (x.x%)
Abnormal (CS)	xx (x.x%)	xx (x.x%)	xx (x.x%)	xx (x.x%)	xx (x.x%)	xx (x.x%)	xx (x.x%)	xx (x.x%)	xx (x.x%)	xx (x.x%)	xx (x.x%)	xx (x.x%)
Total	xx (x.x%)	xx (x.x%)	xx (x.x%)	xx (x.x%)	xx (x.x%)	xx (x.x%)	xx (x.x%)	xx (x.x%)	xx (x.x%)	xx (x.x%)	xx (x.x%)	xx (x.x%)

Shift from Baseline (x.x%) = proportion of subjects

Version 1.1 31-May-2023

Confidential Page 54/58

Table 14.4.2.3 Physical Exam Shift Tables

Parameter: e.g., Respiratory System												
	PraB 40 (n = xx) Baseline				PraB 20 (n = xx) Baseline				OnaB 20 (n = xx) Baseline			
Timepoint	Normal	Abnormal (NCS)	Abnormal (CS)	Total	Normal	Abnormal (NCS)	Abnormal (CS)	Total	Normal	Abnormal (NCS)	Abnormal (CS)	Total
V3 (48hr)												
Normal	xx (x.x%)	xx (x.x%)	xx (x.x%)	xx (x.x%)	xx (x.x%)	xx (x.x%)	xx (x.x%)	xx (x.x%)	xx (x.x%)	xx (x.x%)	xx (x.x%)	xx (x.x%)
Abnormal (NCS)	xx (x.x%)	xx (x.x%)	xx (x.x%)	xx (x.x%)	xx (x.x%)	xx (x.x%)	xx (x.x%)	xx (x.x%)	xx (x.x%)	xx (x.x%)	xx (x.x%)	xx (x.x%)
Abnormal (CS)	xx (x.x%)	xx (x.x%)	xx (x.x%)	xx (x.x%)	xx (x.x%)	xx (x.x%)	xx (x.x%)	xx (x.x%)	xx (x.x%)	xx (x.x%)	xx (x.x%)	xx (x.x%)
Total	xx (x.x%)	xx (x.x%)	xx (x.x%)	xx (x.x%)	xx (x.x%)	xx (x.x%)	xx (x.x%)	xx (x.x%)	xx (x.x%)	xx (x.x%)	xx (x.x%)	xx (x.x%)
V5 (D30)												
Normal	xx (x.x%)	xx (x.x%)	xx (x.x%)	xx (x.x%)	xx (x.x%)	xx (x.x%)	xx (x.x%)	xx (x.x%)	xx (x.x%)	xx (x.x%)	xx (x.x%)	xx (x.x%)
Abnormal (NCS)	xx (x.x%)	xx (x.x%)	xx (x.x%)	xx (x.x%)	xx (x.x%)	xx (x.x%)	xx (x.x%)	xx (x.x%)	xx (x.x%)	xx (x.x%)	xx (x.x%)	xx (x.x%)
Abnormal (CS)	xx (x.x%)	xx (x.x%)	xx (x.x%)	xx (x.x%)	xx (x.x%)	xx (x.x%)	xx (x.x%)	xx (x.x%)	xx (x.x%)	xx (x.x%)	xx (x.x%)	xx (x.x%)
Total	xx (x.x%)	xx (x.x%)	xx (x.x%)	xx (x.x%)	xx (x.x%)	xx (x.x%)	xx (x.x%)	xx (x.x%)	xx (x.x%)	xx (x.x%)	xx (x.x%)	xx (x.x%)
••••												
Normal	xx (x.x%)	xx (x.x%)	xx (x.x%)	xx (x.x%)	xx (x.x%)	xx (x.x%)	xx (x.x%)	xx (x.x%)	xx (x.x%)	xx (x.x%)	xx (x.x%)	xx (x.x%)
Abnormal (NCS)	xx (x.x%)	xx (x.x%)	xx (x.x%)	xx (x.x%)	xx (x.x%)	xx (x.x%)	xx (x.x%)	xx (x.x%)	xx (x.x%)	xx (x.x%)	xx (x.x%)	xx (x.x%)
Abnormal (CS)	xx (x.x%)	xx (x.x%)	xx (x.x%)	xx (x.x%)	xx (x.x%)	xx (x.x%)	xx (x.x%)	xx (x.x%)	xx (x.x%)	xx (x.x%)	xx (x.x%)	xx (x.x%)
Total	xx (x.x%)	xx (x.x%)	xx (x.x%)	xx (x.x%)	xx (x.x%)	xx (x.x%)	xx (x.x%)	xx (x.x%)	xx (x.x%)	xx (x.x%)	xx (x.x%)	xx (x.x%)
V16 (D365)												
Normal	xx (x.x%)	xx (x.x%)	xx (x.x%)	xx (x.x%)	xx (x.x%)	xx (x.x%)	xx (x.x%)	xx (x.x%)	xx (x.x%)	xx (x.x%)	xx (x.x%)	xx (x.x%)
Abnormal (NCS)	xx (x.x%)	xx (x.x%)	xx (x.x%)	xx (x.x%)	xx (x.x%)	xx (x.x%)	xx (x.x%)	xx (x.x%)	xx (x.x%)	xx (x.x%)	xx (x.x%)	xx (x.x%)
Abnormal (CS)	xx (x.x%)	xx (x.x%)	xx (x.x%)	xx (x.x%)	xx (x.x%)	xx (x.x%)	xx (x.x%)	xx (x.x%)	xx (x.x%)	xx (x.x%)	xx (x.x%)	xx (x.x%)
Total	xx (x.x%)	xx (x.x%)	xx (x.x%)	xx (x.x%)	xx (x.x%)	xx (x.x%)	xx (x.x%)	xx (x.x%)	xx (x.x%)	xx (x.x%)	xx (x.x%)	xx (x.x%)

Shift from Baseline (x.x%) = proportion of subjects

[figure not shown]
Confidential Page 55/58

14.4.3 Directed Review of Systems

Table 14.4.3.1 Directed Review of Systems

Parameter: e.g.,	Parameter: e.g., Head and Neck											
	PraB 40 (n = xx) Baseline				PraB 20 (n = xx) Baseline			OnaB 20 (n = xx) Baseline				
Timepoint	Normal	Abnormal (NCS)	Abnormal (CS)	Total	Normal	Abnormal (NCS)	Abnormal (CS)	Total	Normal	Abnormal (NCS)	Abnormal (CS)	Total
V3 (48hr)												
Normal	xx (x.x%)	xx (x.x%)	xx (x.x%)	xx (x.x%)	xx (x.x%)	xx (x.x%)	xx (x.x%)	xx (x.x%)	xx (x.x%)	xx (x.x%)	xx (x.x%)	xx (x.x%)
Abnormal (NCS)	xx (x.x%)	xx (x.x%)	xx (x.x%)	xx (x.x%)	xx (x.x%)	xx (x.x%)	xx (x.x%)	xx (x.x%)	xx (x.x%)	xx (x.x%)	xx (x.x%)	xx (x.x%)
Abnormal (CS)	xx (x.x%)	xx (x.x%)	xx (x.x%)	xx (x.x%)	xx (x.x%)	xx (x.x%)	xx (x.x%)	xx (x.x%)	xx (x.x%)	xx (x.x%)	xx (x.x%)	xx (x.x%)
Total	xx (x.x%)	xx (x.x%)	xx (x.x%)	xx (x.x%)	xx (x.x%)	xx (x.x%)	xx (x.x%)	xx (x.x%)	xx (x.x%)	xx (x.x%)	xx (x.x%)	xx (x.x%)
V5 (D30)												
Normal	xx (x.x%)	xx (x.x%)	xx (x.x%)	xx (x.x%)	xx (x.x%)	xx (x.x%)	xx (x.x%)	xx (x.x%)	xx (x.x%)	xx (x.x%)	xx (x.x%)	xx (x.x%)
Abnormal (NCS)	xx (x.x%)	xx (x.x%)	xx (x.x%)	xx (x.x%)	xx (x.x%)	xx (x.x%)	xx (x.x%)	xx (x.x%)	xx (x.x%)	xx (x.x%)	xx (x.x%)	xx (x.x%)
Abnormal (CS)	xx (x.x%)	xx (x.x%)	xx (x.x%)	xx (x.x%)	xx (x.x%)	xx (x.x%)	xx (x.x%)	xx (x.x%)	xx (x.x%)	xx (x.x%)	xx (x.x%)	xx (x.x%)
Total	xx (x.x%)	xx (x.x%)	xx (x.x%)	xx (x.x%)	xx (x.x%)	xx (x.x%)	xx (x.x%)	xx (x.x%)	xx (x.x%)	xx (x.x%)	xx (x.x%)	xx (x.x%)
••••												
Normal	xx (x.x%)	xx (x.x%)	xx (x.x%)	xx (x.x%)	xx (x.x%)	xx (x.x%)	xx (x.x%)	xx (x.x%)	xx (x.x%)	xx (x.x%)	xx (x.x%)	xx (x.x%)
Abnormal (NCS)	xx (x.x%)	xx (x.x%)	xx (x.x%)	xx (x.x%)	xx (x.x%)	xx (x.x%)	xx (x.x%)	xx (x.x%)	xx (x.x%)	xx (x.x%)	xx (x.x%)	xx (x.x%)
Abnormal (CS)	xx (x.x%)	xx (x.x%)	xx (x.x%)	xx (x.x%)	xx (x.x%)	xx (x.x%)	xx (x.x%)	xx (x.x%)	xx (x.x%)	xx (x.x%)	xx (x.x%)	xx (x.x%)
Total	xx (x.x%)	xx (x.x%)	xx (x.x%)	xx (x.x%)	xx (x.x%)	xx (x.x%)	xx (x.x%)	xx (x.x%)	xx (x.x%)	xx (x.x%)	xx (x.x%)	xx (x.x%)
V16 (D365)												
Normal	xx (x.x%)	xx (x.x%)	xx (x.x%)	xx (x.x%)	xx (x.x%)	xx (x.x%)	xx (x.x%)	xx (x.x%)	xx (x.x%)	xx (x.x%)	xx (x.x%)	xx (x.x%)
Abnormal (NCS)	xx (x.x%)	xx (x.x%)	xx (x.x%)	xx (x.x%)	xx (x.x%)	xx (x.x%)	xx (x.x%)	xx (x.x%)	xx (x.x%)	xx (x.x%)	xx (x.x%)	xx (x.x%)
Abnormal (CS)	xx (x.x%)	xx (x.x%)	xx (x.x%)	xx (x.x%)	xx (x.x%)	xx (x.x%)	xx (x.x%)	xx (x.x%)	xx (x.x%)	xx (x.x%)	xx (x.x%)	xx (x.x%)
Total	xx (x.x%)	xx (x.x%)	xx (x.x%)	xx (x.x%)	xx (x.x%)	xx (x.x%)	xx (x.x%)	xx (x.x%)	xx (x.x%)	xx (x.x%)	xx (x.x%)	xx (x.x%)

Shift from Baseline (x.x%) = proportion of subjects

Confidential Page 56/58

14.4.4 Vital Signs

Table 14.4.4.1 Vital Signs - SBP

V1 (BL)	PraB 40	PraB 20	OnaB 20
	$(\mathbf{n} = \mathbf{x}\mathbf{x})$	$(\mathbf{n} = \mathbf{x}\mathbf{x})$	$(\mathbf{n} = \mathbf{x}\mathbf{x})$
V1 (BL)	$xxx.x \pm xx.x$	$xxx.x \pm xx.x$	$xxx.x \pm xx.x$
SBP (mean \pm SD)	$xxx.x \pm xx.x$	$xxx.x \pm xx.x$	$xxx.x \pm xx.x$
V3 (48hr)			
SBP (mean \pm SD)	$xxx.x \pm xx.x$	$xxx.x \pm xx.x$	$xxx.x \pm xx.x$
Δ from BL	$xx.x \pm xx.x$	$xx.x \pm xx.x$	$xx.x \pm xx.x$
••••			
SBP (mean \pm SD)	$xxx.x \pm xx.x$	$xxx.x \pm xx.x$	$xxx.x \pm xx.x$
Δ from BL	$xx.x \pm xx.x$	$xx.x \pm xx.x$	$xx.x \pm xx.x$
Normal	xx (x.x%)	xx (x.x%)	xx (x.x%)

Table 14.4.4.2 Vital Signs - DBP

V1 (BL)	PraB 40 (n = xx)	PraB 20 (n = xx)	OnaB 20 (n = xx)
V1 (BL)	$xxx.x \pm xx.x$	$xxx.x \pm xx.x$	$xxx.x \pm xx.x$
DBP (mean \pm SD)	$xxx.x \pm xx.x$	$xxx.x \pm xx.x$	$xxx.x \pm xx.x$
V3 (48hr)			
DBP (mean \pm SD)	$xxx.x \pm xx.x$	$xxx.x \pm xx.x$	$xxx.x \pm xx.x$
Δ from BL	$xx.x \pm xx.x$	$xx.x \pm xx.x$	$xx.x \pm xx.x$
••••			
DBP (mean \pm SD)	$xxx.x \pm xx.x$	$xxx.x \pm xx.x$	$xxx.x \pm xx.x$
Δ from BL	$xx.x \pm xx.x$	$xx.x \pm xx.x$	$xx.x \pm xx.x$
Normal	xx (x.x%)	xx (x.x%)	xx (x.x%)

Table 14.4.4.3 Vital Signs - HR

V1 (BL)	PraB 40	PraB 20	OnaB 20
	$(\mathbf{n} = \mathbf{x}\mathbf{x})$	$(\mathbf{n} = \mathbf{x}\mathbf{x})$	$(\mathbf{n} = \mathbf{x}\mathbf{x})$
V1 (BL)	$xxx.x \pm xx.x$	$xxx.x \pm xx.x$	$xxx.x \pm xx.x$
HR (mean \pm SD)	$xxx.x \pm xx.x$	$xxx.x \pm xx.x$	$xxx.x \pm xx.x$
V3 (48hr)			
HR (mean \pm SD)	$xxx.x \pm xx.x$	$xxx.x \pm xx.x$	$xxx.x \pm xx.x$
Δ from BL	$xx.x \pm xx.x$	$xx.x \pm xx.x$	$xx.x \pm xx.x$
••••			
HR (mean \pm SD)	$xxx.x \pm xx.x$	$xxx.x \pm xx.x$	$xxx.x \pm xx.x$
Δ from BL	$xx.x \pm xx.x$	$xx.x \pm xx.x$	$xx.x \pm xx.x$
Normal	xx (x.x%)	xx (x.x%)	xx (x.x%)

Table 14.4.4.4 Vital Signs – Respiratory Rate (RR)

V1 (BL)	PraB 40 (n = xx)	PraB 20 (n = xx)	OnaB 20 (n = xx)
V1 (BL)	$xxx.x \pm xx.x$	$xxx.x \pm xx.x$	$xxx.x \pm xx.x$
RR (mean \pm SD)	$xxx.x \pm xx.x$	$xxx.x \pm xx.x$	$xxx.x \pm xx.x$
V3 (48hr)			
RR (mean \pm SD)	$xxx.x \pm xx.x$	$xxx.x \pm xx.x$	$xxx.x \pm xx.x$
Δ from BL	$xx.x \pm xx.x$	$xx.x \pm xx.x$	$xx.x \pm xx.x$
••••			
RR (mean \pm SD)	$xxx.x \pm xx.x$	$xxx.x \pm xx.x$	$xxx.x \pm xx.x$
Δ from BL	$xx.x \pm xx.x$	$xx.x \pm xx.x$	$xx.x \pm xx.x$
Normal	xx (x.x%)	xx (x.x%)	xx (x.x%)

14.4.5 Vital Signs

Table 14.4.5.1 Directed Questionnaire

	Pra	B 40	Pra	B 20	OnaB 20		
	(n =	= xx)	(n =	xx)	(n =	· xx)	
V1 (BL)	Yes	No	Yes	No	Yes	No	
Speaking	xx (x.x%)						
Swallowing	xx (x.x%)						
Breathing	xx (x.x%)						
Headaches	xx (x.x%)						
Eyelid Drooping	xx (x.x%)						
Eyebrow Drooping	xx (x.x%)						
V3 (48hr)							
Speaking	xx (x.x%)						
Swallowing	xx (x.x%)						
Breathing	xx (x.x%)						
Headaches	xx (x.x%)						
Eyelid Drooping	xx (x.x%)						
Eyebrow Drooping	xx (x.x%)						
V5 (D30)							
Speaking	xx (x.x%)						
Swallowing	xx (x.x%)						
Breathing	xx (x.x%)						
Headaches	xx (x.x%)						
Eyelid Drooping	xx (x.x%)						
Eyebrow Drooping	xx (x.x%)						
••••							
Speaking	xx (x.x%)						
Swallowing	xx (x.x%)						
Breathing	xx (x.x%)						
Headaches	xx (x.x%)						
Eyelid Drooping	xx (x.x%)						
Eyebrow Drooping	xx (x.x%)						

Shift from Baseline

(x.x%) = proportion of subjects

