6. SAFETY ASSESSMENTS

6.1. Directed Questionnaire

The following questions will be asked looking for signs of local or distant botulinum toxin spread and to set a baseline:

- Have you noticed any problems with speaking, swallowing, or breathing?
- Have you had any headaches, eyelid or eyebrow drooping?

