7.4.3. Vital Signs

The number and percentage of subjects with a clinically significant vital sign abnormality (Investigator opinion) will be summarized for each parameter; percentages will be based on subjects with non-missing values.

Descriptive statistics will be used to summarize observed values and changes from Baseline. Tabular and graphical methods may be used to present results for parameters of interest. Listings will be provided with flags indicating clinically significant abnormalities.

7.4.4. 12-Lead ECGs

The number and percentage of subjects with a clinically significant ECG abnormality (Investigator opinion) will be summarized for each parameter; percentages will be based on subjects with non-missing values.

Descriptive statistics will be used to summarize results and changes from Baseline. Tabular and graphical methods may be used to present results for parameters of interest. Listings will be provided with flags indicating clinically significant abnormalities.

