7.7. General Considerations

Data will be listed by subject number. Data will be summarized by treatment and study visit, where applicable. For categorical parameters, the number and percentage of subjects/observations in each category will be presented; percentages will be based on the number of subjects in the relevant analysis population in each treatment group. For continuous parameters, descriptive statistics will include n (number of subjects or observations), mean, standard deviation, median, and range. A full description of the statistical methods planned for this study will be provided in the Statistical Analysis Plan (SAP). All programs for data output and analyses will be written in SAS version 9.4 or higher (SAS Institute, Inc., Cary, NC).

Missing Values: For the mITT analysis of primary, secondary, tertiary, and exploratory duration of effectiveness endpoints, in the case of a missed visit, subjects will be considered to have returned to Baseline if they are confirmed to have returned to Baseline at the next non-missed visit. Subjects will be considered to have to have returned to Baseline if they fail to attend 2 consecutive visits or drop out of the study. For missing observations for exploratory endpoints other than duration of effect data will be analyzed as observed without imputation.

Discontinuation and Drop-Outs: Dropouts will not be replaced. Subject disposition will summarize the number of subjects who were randomized and who discontinued from the study (including reasons for discontinuation).

Interim Analysis: An interim analysis will be conducted when >90% of subjects have completed Visit 8 (Day 120) to evaluate response to exposure (efficacy, duration) and adverse events. For assessment of the primary effectiveness endpoint, 95% CIs will be presented but statistical analyses will not be conducted and a statistical penalty for the final analysis will not be employed. While data by treatment group will be presented, individual subjects will not be unblinded.

Poolability of Investigative Sites: Data from all investigative sites will be pooled based on the assumption of clinical comparability: the same protocol will be used for all sites, all sites will be monitored for protocol compliance, and the same data collection instrument and methodology will be used across all sites.

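### The Directed Questionnaire table is labelled a shift table but prints only Yes/No totals per visit, over a denominator that does not follow attendance

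*SAP*

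**What the plan says.** SAP 6.1 gives the purpose of the instrument: "The following questions will be asked looking for signs of local or distant botulinum toxin spread and to set a baseline". The items cover speaking, swallowing, breathing, headache, and eyelid or eyebrow drooping. The protocol synopsis lists the questionnaire among the safety endpoints.

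The only output planned for it is "Table 14.4.5.1 Directed Questionnaire". For each arm, the shell has Yes and No columns and one row per symptom at V1, V3, V5 and later visits. The footnote reads "Shift from Baseline". The section heading above the table is 14.4.5 Vital Signs, although vital signs are in 14.4.4.

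SAP 7.4 describes AE, laboratory, vital-sign and ECG summaries but no questionnaire analysis, so the shell is the whole specification.

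On denominators, SAP 7.7 sets the general rule for categorical data: "percentages will be based on the number of subjects in the relevant analysis population in each treatment group". SAP 7.4.3 and 7.4.4 depart from it for vital signs and ECG: "percentages will be based on subjects with non-missing values". No such exception is made for the questionnaire.

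**The concern.** A baseline answer is useful only if each later answer is compared with it, subject by subject. This table prints the baseline row and then makes no such comparison, while its footnote tells the reader that it has. Totals can stay flat while some subjects lose a complaint and others acquire one.

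The denominator adds a second distortion. Subjects leave the study when their lines return to Baseline, so later visits hold fewer subjects, and fewer still in an arm whose effect wears off sooner. Dividing by the full arm then understates the complaint rate by different amounts in different arms.

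What is at stake is the readability of one safety table, in a trial where the safety of 40U is a primary objective.

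**Working it through.** The plan states no figure on this point, so there is none to reproduce. The check compares layouts and then bounds what the printed totals can tell.

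**1. Layouts side by side.** "Table 14.4.3.1 Directed Review of Systems" has the same footnote. Its shell puts Baseline status in columns and visit status in rows, so each change of state has its own cell. The laboratory, ECG and Physical Exam shells (14.4.2.1 to 14.4.2.3) do the same. Table 14.4.5.1 has no Baseline dimension.

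**2. New onset at one visit.** Let N subjects answer at both visits, B say Yes at V1 and P say Yes at the later visit. The number going from No to Yes lies between max(0, P − B) and min(P, N − B). N = 50 is the planned arm size (SAP 7.6). B and P are assumptions, because the documents give no symptom rates.

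| B (V1 Yes) | P (visit Yes) | New cases that fit |
|---|---|---|
| 0 | 3 | exactly 3 |
| 2 | 2 | 0 to 2 |
| 5 | 8 | 3 to 8 |
| 10 | 10 | 0 to 10, i.e. 0 to 25% of the 40 at risk |

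The ambiguity vanishes when B = 0 and grows with B.

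**3. Distinct subjects across visits.** Even with B = 0, 2 Yes at V3 and 2 Yes at V5 fit anything from 2 subjects (the same two) to 4 (all different).

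**4. Denominator.** Inputs from SAP 7.6: exponential times, reference median 4 months, hazard ratio 0.47, annual censoring 10%, 50 per arm. Assumptions: the reference values apply to the 20U prabotulinumtoxinA arm, and a subject attends Day 180 if neither returned to Baseline nor dropped out by the Day 150 visit.

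- Loss-of-effect hazard: ln 2 / 4 = 0.1733 per month on 20U; × 0.47 = 0.0814 on 40U.
- Dropout hazard: −ln(0.9) / 12 = 0.0088 per month.
- 150 days = 4.93 months.
- 20U: 50 × exp(−(0.1733 + 0.0088) × 4.93) = about 20.4 attending.
- 40U: 50 × exp(−(0.0814 + 0.0088) × 4.93) = about 32.1 attending.

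If 10% of attendees complain in each arm (assumption), the printed values are 2.04 / 50 = 4.1% and 3.21 / 50 = 6.4%. At Day 330 the same model gives 8.3 and 20.5 attending, so an identical 10% prints as 1.7% and 4.1%.

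**5. Window for an ever-affected count.** Counting any post-dose Yes over the whole study gives more chances to the arm that stays longer. Under the same model, with exit at return to Baseline and no Day 90 floor, the expected questionnaire visits are about 6.4 (20U) and 8.7 (40U). An identical 5% chance of a new Yes at each visit (assumption) gives about 27% against 35% ever affected. Limited to the four visits at 48 hours and Days 30, 60 and 90, with all attended, it gives 1 − 0.95⁴ = 18.5% in each arm.

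**The case against.** A reader might infer that the trial has no other way to see toxin spread or new symptoms. The documents do not support that. The Directed Review of Systems and the Physical Exam, the latter with cranial nerve and muscle-weakness assessment, are done at the same in-person follow-up visits and have genuine shift tables. Treatment-emergent AEs are tabulated by preferred term and arm with 95% CIs, and Protocol 10.5.1 keeps pre-existing symptoms out unless they worsen. An AESI table covers swallowing, breathing and speech events. By-subject listings are planned as well. This objection largely stands. What it leaves is that the protocol requires clinically significant laboratory and ECG findings to be reported as AEs but has no such rule for a questionnaire Yes, and that the AESI list does not include headache.

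A reader might also infer that new ptosis is hidden. It is not, in practice: exclusion 6 removes subjects with current or past eyelid or eyebrow ptosis, so V1 Yes should be near zero and each visit's Yes count is close to new onset. The same holds for speaking, swallowing and breathing if their printed V1 rows are zero. Headache is the clear remaining case, since no criterion excludes it and the question has no recall window.

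On the denominator, adding Yes and No recovers the number who answered, so attendance is not lost. That is correct, but the printed percentages still mislead. Finally, the symptom rates used here are assumed and safety data are summarised descriptively, so no planned test changes. That also stands.

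**Conclusion.** The point holds as a minor safety-table defect. The footnote and the shell disagree. As laid out, the table cannot separate new from pre-existing complaints for any symptom with Yes answers at V1, and it cannot count distinct subjects affected over time. The SAP 7.7 denominator understates later-visit rates, and more so in arms whose subjects exit earlier.

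The size depends on assumptions: 0 to 10 new headaches behind one row if 10 of 50 have headache at V1, and 4.1% against 6.4% for equal Day 180 rates under the sample-size inputs. The problem affects all three arms. It does not mean that the safety of 40U goes unassessed, and it touches neither power, alpha nor the primary effectiveness result.

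**What to change.** 1. For each questionnaire item, replace the shell with the Baseline-by-visit cross-tabulation already used in Table 14.4.3.1.
2. Print the number assessed at each visit and use it as the denominator, as SAP 7.4.3 and 7.4.4 do.
3. For each item and arm, add the subjects answering No at V1 and Yes at any post-dose visit through Day 90, over those answering No at V1, with a 95% CI. Day 90 is the common follow-up window under Protocol 10.2.5, which ties eligibility to exit to that visit. Protocol 4.1 and SAP 2.1 describe exit at return to Baseline without that floor, so these passages must be reconciled; meanwhile, print how many subjects reached each visit.
4. Correct the 14.4.5 heading to name the Directed Questionnaire.

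The cost is one table shell and its program. No new data are needed.

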14.4.6 Antitoxin Antibodies

Table 14.4.6.1 Presence of Antibodies

	Pral			B 20	OnaB 20 (n = xx)		
	Yes No		Yes	$\frac{(n = xx)}{Yes} \qquad No$		No	
V1 (BL)	n=	XX	n=	XX	n=xx		
	xx (x.x%)	xx (x.x%)	xx (x.x%)	xx (x.x%)	xx (x.x%)	xx (x.x%)	
V3 (48hr)	n=xx		n=	XX	n=xx		
	xx (x.x%)	xx (x.x%)	xx (x.x%)	xx (x.x%)	xx (x.x%)	xx (x.x%)	
V5 (D30	n=	XX	n=	XX	n=xx		
	xx (x.x%)	xx (x.x%)	xx (x.x%)	xx (x.x%)	xx (x.x%)	xx (x.x%)	
V6 (D60)	n=	XX	n=xx		n=xx		
	xx (x.x%)	xx (x.x%)	xx (x.x%)	xx (x.x%)	xx (x.x%)	xx (x.x%)	
••••	n=xx		n=	XX	n=xx		
	xx (x.x%)	xx (x.x%)	xx (x.x%)	xx (x.x%)	xx (x.x%)	xx (x.x%)	

xx (x.x%) = number of subjects (proportion of subjects)
